# 9. Investigational Product

#### 9.1 About Ferinject ® (FCM)

FCM is a polynuclear iron (III)-hydroxide carbohydrate complex. FCM has been designed to enable controlled, systemic release of iron within cells of the reticuloendothelial system, minimizing the risk of releasing large amounts of iron into the serum.

The structure of polynuclear iron (III) hydroxide core resembles that of ferritin: the iron is trapped in the core in a non-redox active form and, therefore, toxic effects from weakly-bound iron are limited. The complex has an average molecular weight of 150,000 Da.

Following IV administration, FCM is metabolized by the RES in the spleen and the liver and the iron is delivered to the bone marrow.

#### Adverse drug reactions observed during clinical trials and post-marketing experience:

| System Organ Class                                   | Common (≥1/100 to <1/10)                | Uncommon (≥1/1000 to <1/100)                                       | Rare (≥1/10000 to <1/1000)   |
|--|---|--|--|
| Immune system disorders                              |   | Hypersensitivity   | Anaphylactoid reactions  |
| Nervous system disorders                             | Headache, dizziness                     | Paraesthesia, dysgeusia  | Loss of consciousness    |
| Psychiatric disorders                                |   |  | Anxiety    |
| Cardiac disorders                                    |   | Tachycardia  |  |
| Vascular disorders                                   | Hypertension                            | Hypotension, flushing  | Phlebitis, syncope  , presyncope                       |
| Respiratory, thoracic and mediastinal disorders      |   | Dyspnoea   | Bronchospasm   |
| Gastrointestinal disorders                           | Nausea                                  | Vomiting, dyspepsia,
abdominal pain,
constipation, diahorrea | Flatulence   |
| Skin and subcutaneous tissue disorders               |   | Pruritus, urticaria,
erythema, rash               | Angioedema  , pallor  , and face oedema  |
| Musculoskeletal and connective tissue disorders      | _                                       | Myalgia, back pain, arthralgia, muscle spasms                      |  |
| General disorders and administration site conditions | Injection site reactions  | Pyrexia, fatigue, chest pain, oedema peripheral, chills            | Rigors, malaise  |

PRT-INM-0615/09 V06

| System Organ Class                   | Common (≥1/100 to <1/10)           | Uncommon (≥1/1000 to <1/100)  | Rare (≥1/10000 to <1/1000) |  |  |
|--------------------------------------|------------------------------------|---|----------------------------|--|--|
| Investigations                       | Alanine aminotransferase increased | Aspartate aminotransferase increased, gamma- glutamyltransferase increased, blood lactate dehydrogenase increased, blood alkaline phosphatase increased |                            |  |  |
| Metabolism and nutritional disorders | Hypophosphataemia                  |   |                            |  |  |

- 1 Includes the following preferred terms: rash (individual ADR frequency determined as uncommon) and rash erythematous, -generalised, -macular, -maculo-papular, -pruritic (all individual ADRs are frequency determined as rare).
- 2 Includes the following preferred terms: infusion site burning, -pain, -bruising, -discolouration, -extravasation, -irritation, reaction, (all individual ADRs are frequency determined as uncommon) and -paraesthesia (individual ADR frequency determined as rare).
- 3 ADRs exclusively reported in the post-marketing setting.
- 4 ADRs reported in the post-marketing setting which were also observed in the clinical setting.

Note: ADR = Adverse drug reaction.

#### 9.2 Storage, Dispensing and Accountability

The study product will be stored in a secure drug cabinet at KHCC outpatient pharmacy at less than 30 °C. The storage area is separate from the rest of products within the pharmacy. It is access limited to a dedicated Investigational Drug Pharmacist (IDP) who will be responsible to dispense the product for use in the study. Storage conditions will be monitored throughout the study and if there are aberrant conditions they will be reported, justified and corrected as seen appropriate.

Dispensing will be based on paper prescriptions signed by the investigator. The IDP will dispense the required vials to the clinical research coordinator (CRC). The IDP will track product dispensing through the accountability logs. Product documentation for shipment, storage and allocation will be maintained in the pharmacy files until end of study. Documents will then be transferred to the trial master file (TMF).

#### 9.3 Dose and Administration

FCM will be administered based on the following:

| 5 11 11 ( / / 11)  | Body Weight (Kg) |         |  |  |
|--------------------|------------------|---------|--|--|
| Baseline Hb (g/dL) | <70              | >70     |  |  |
| <10                | 1500 mg          | 2000 mg |  |  |
| ≥ 10        | 1000 mg          | 1500 mg |  |  |

#### 9.4 Stopping Rules

There are no formal stopping rules for the study but should the patient develop anaphylaxis or para-venous leak is observed, the infusion will be interrupted and patient treatment will be left to the attending physician.

## 10. Procedures and Assessments

All study procedures will be conducted at KHCC. The investigator and supporting study team will be responsible to document all related procedures and assessments done in the appropriate source document and the patient CRFs. All procedures and assessments will support the safety and validity of conclusions drawn from the study protocol.

#### 10.1 Screening and Baseline

Patients will be invited to participate in the study once they are diagnosed as anemic and are planned to receive chemotherapy or radiotherapy within seven days. The Investigator will discuss the study with the patient and acquire a written informed consent before starting any study related procedure. If the patient agrees to participate the following will be carried out:

- 1. Obtaining medical and oncologic history
- 2. Physical Examination
- 3. Vital Signs
- 4. Laboratory assessments will include:
  - Hemoglobin, reticulocyte count
  - · Serum iron, ferritin, total iron binding capacity, TSAT
  - Vitamin B12, folate
  - Creatinine
  - Phosphorous
  - Liver function test including: total bilirubin, ALT, AST, LDH, GGT
  - Serum Hepcidin
  - CRP
  - Pregnancy test
- 5. Evaluation of ECOG performance status

#### **10.2 Treatment phase**

[figure not shown]
- Patients will receive their prescribed FCM infusion in the KHCC infusion areas or in the inpatients units.
- FCM will be administered as a single infusion if the needed dose is 1000 mg as a short IV infusion, diluted in 250mL of 0.9 saline over 15-30 minutes.

- If the needed FCM dose is > 1000 mg, an initial dose of 1000 mg will be given as above and the remaining dose will be given the week after in a similar fashion if the remaining dose is 1000mg; if the remaining dose is 500mg, then it will be given as a short IV infusion, diluted in 100mL of 0.9 saline over a minimum period of 6 minutes.
- During the infusion, the patient will be monitored for adverse events.

#### 10.3 Follow-up

- Hemoglobin assessments will be carried out every 3 weeks in line with the chemotherapy protocol visits and at week 12.
- Laboratory monitoring of ALT, AST, LDH, Alk-phosphatase, GGT and phosphorous will be done at week-3
- Ferritin level will be repeated at week-12
- A total of four follow-up visits are required for the study: weeks 3, 6, 9 and 12.

Figure 1 Study Scheme

**Table 1 Study Procedures Schedule** 

| Procedure                           | Screening
Phase | Treatment Phase |                    | Follow up Phase    |                    |                    |                     |
|-------------------------------------|--------------------|-----------------|--------------------|--------------------|--------------------|--------------------|---------------------|
|                                     | Week-0             | Week-1          | Week-2             | Week 3
± 3 days | Week 6
± 3 days | Week 9
± 3 days | Week 12
± 3 days |
| Medical and oncologic history       | х                  |                 |                    |                    |                    |                    |                     |
| Physical Examination                | Х                  |                 |                    | Х                  | Х                  | Х                  | Х                   |
| ECOG performance status             | Х                  |                 |                    | Х                  | Х                  | Х                  | Х                   |
| Vital Signs                         | Х                  |                 |                    | Х                  | Χ                  | Х                  | Х                   |
| Hb                                  | Х                  |                 |                    | Х                  | Χ                  | Х                  | Х                   |
| Reticulocyte count                  | Х                  |                 |                    |                    |                    |                    |                     |
| Serum iron                          | Х                  |                 |                    |                    |                    |                    |                     |
| Serum ferritin                      | Х                  |                 |                    |                    |                    |                    | Х                   |
| Total Iron Binding Capacity (TIBC)  | х                  |                 |                    |                    |                    |                    |                     |
| TSAT                                | Х                  |                 |                    |                    |                    |                    |                     |
| Hepcidin levels                     | Х                  |                 |                    |                    |                    |                    |                     |
| CRP                                 | Х                  |                 |                    |                    |                    |                    |                     |
| vitamin B12                         | Х                  |                 |                    |                    |                    |                    |                     |
| Folate                              | Х                  |                 |                    |                    |                    |                    |                     |
| Creatinine                          | Х                  |                 |                    |                    |                    |                    |                     |
| Bilirubin total                     | Х                  |                 |                    |                    |                    |                    |                     |
| AST                                 | Х                  |                 |                    | X                  |                    |                    |                     |
| ALT                                 | X                  |                 |                    | X                  |                    |                    |                     |
| Alkaline phosphatase                | Х                  |                 |                    | X                  |                    |                    |                     |
| Gamma-
glutamyltransferase (GGT) | х                  |                 |                    | Х                  |                    |                    |                     |
| LDH                                 | Х                  |                 |                    | Х                  |                    |                    |                     |
| Phosphorous level                   | Х                  |                 |                    | Х                  |                    |                    |                     |
| B-hCG (pregnancy test)              | Х                  |                 |                    |                    |                    |                    |                     |
| Monitoring of adverse events        | Х                  |                 |                    | х                  | Х                  | х                  | х                   |
| FCM infusion                        |                    | Х               | X
(when needed) |                    |                    |                    |                     |

## 11. Adverse events

The best effort will be done by the investigator or study supporting staff to record all adverse events that arise during the study with possible causality and relationship to the study treatment. The proper channels to process these events will be as described in this section. All adverse events reporting will be done with reference to ICH E6: Guidance on Good Clinical Practice and the ICH E2D: Post Approval Safety Data Management, and in-house policies.

#### 11.1 Definitions

Adverse Event (AE): any untoward medical occurrence in a patient or clinical investigation subject administered a pharmaceutical product and which does not necessarily have a causal relationship with this treatment. An adverse event can therefore be any unfavorable and unintended sign (including an abnormal laboratory finding), symptom, or disease temporarily associated with the use of a medicinal (investigational) product, whether or not related to the medicinal (investigational) product.

**Adverse Drug Reaction (ADR):** all noxious and unintended responses to a medicinal product related to any dose should be considered adverse drug reactions.

The phrase 'responses to a medicinal product' means that a causal relationship between a medicinal product and an adverse event is at least a reasonable possibility i.e. the relationship cannot be ruled out.

Regarding marketed medicinal products, a response to a drug which is noxious and unintended and which occurs at doses normally used in man for prophylaxis, diagnosis, or therapy of diseases or for modification of physiologic function.

A reaction, in contrast to an event, is characterized by the fact that a causal relationship between the drug and the occurrence is suspected. For regulatory reporting purposes, if an event is spontaneously reported, even if the relationship is unknown or unstated, it meets the definition of an adverse drug reaction.

Serious Adverse Events (SAE) or Serious Adverse Drug Reaction (Serious ADR): any untoward medical occurrence that at any dose:

- Results in death,
- Is life-threatening,
- Requires inpatient hospitalization or prolongation of existing hospitalization,
- Results in persistent or significant disability/incapacity
- is a congenital anomaly/birth defect
- is a medically important event or reaction

**Unexpected ADR:** An ADR whose nature, severity, specificity, or outcome is not consistent with the term or description used in local/regional product labeling (e.g. package insert or summary of product characteristics) should be considered unexpected. If it is uncertain whether the ADR is expected or unexpected, the ADR should be treated as unexpected.

An expected ADR with a fatal outcome should be considered unexpected unless the local/regional product labeling specifically states that the ADR might be associated with a fatal or life threatening outcome.

#### **11.2 Management of Adverse Events**

Standard medical care will be followed in managing adverse events reported during the study in compliance with in house policies and procedures. The PI may ask for additional tests to be done if the adverse event warrants an investigation. The patient will be treated free of charge for all study related events. If the patient is to be discontinued from the study because of the AE he/she will be followed up until the AE abates or returns to baseline.

#### 11.3 Reporting Methodology

All study support staff that are in contact with the patients during the study are responsible to note down any adverse events or complaints reported by patients and report them back to the PI. During their hospital stay, patients will be questioned for adverse events. The team will avoid leading the patient in their adverse event interview. The patient will be asked to describe the severity of their complaint and specify an onset date. Open-ended question will be considered by the study team. The seriousness of the event will be assessed by the investigator and he will determine whether it is expected or unexpected based on the definitions described. Clinical judgment will be used with consideration to the product labeling and known literature.

All AE that are both serious and unexpected will be subject to expedited reporting. For serious unexpected AE with fatal or life threatening consequences, the investigator will notify the JFDA and the institutional review board (IRB) as soon as possible but no later than 7 calendar days from the first time the AE comes to his/her attention. A complete report will be submitted as soon as possible within 8 additional calendar days. Those serious and unexpected ADE/ADR that are not fatal or life threatening will be reported to the JFDA and IRB as soon as possible but no later than 15 calendar days from the first time the AE comes to the knowledge of the investigator with a reasonable suspected causal relationship: A full report will be written to describe the events using the CIOMS I form. The investigator will contact the marketing authorization holder (MAH) of the suspected product with the report in the same manner as would he/she do with the JFDA and IRB if required.

For AE that is not serious whether expected or unexpected do not follow expedited reporting. Within the scope of definitions described above, recording of AE will include description, intensity onset, duration, end and outcome. An evaluation of relationship to the study product will be done according to the following terms: Presence or absence of reasonable possibility that the AE is related to the study drug. AEs will be captured in the case report form. The MAH will not be informed about these AE.

#### 11.4 Follow-up of Adverse Events

All patients will be followed up until recovery or resolution of the AE. The priority for follow-up will be for cases which are 1) serious and unexpected, 2) serious and expected, and 3) non-serious and unexpected. Follow-up information can be through a telephone call and/or site visits (not necessarily related to the predefined study visits or calls). If the patient refuses to provide the information or to come for a follow-up visit it will be indicated in the AE follow-up report. Written confirmation of details given verbally will be obtained whenever possible.

# 12. Data management

#### **12.1 Case Report Forms**

Data for each patient will be compiled in a case report. The case report form used is sufficiently detailed to capture the required information to meet the objectives of the study. Case report form will be retained as part of the TMF and will not have identifiable patient information such as name or medical records number. Case reports forms will be identified with the study ID of the patient.

#### 12.2 Data Entry and the study database

All data from this study that will be used in analysis of primary and secondary endpoints including possible analysis in subgroups of the study population will be transcribed from the subject CRF into an Access database. The transcription of data will be double checked by a member of the support staff that is different from the one entering the data. The database will be designed in house to reflect the subject CRF and the necessary analysis elements. The database will only be used as a reservoir for all the collected data before it is exported into SAS for statistical treatment. Access 2003 or 2007 (2003 compatible mode) database will be used.

#### 12.3 Data Cleaning

Two stages of data cleaning are identified for the study. The first stage is the review of CRFs for missing or misplaced or invalid data before entry into the study database. The second stage is the verification of data entry at the closure of database and before analysis. Queries will be issued by data management to be resolved by the investigator and his team.

Documentation of all queries and corrections made will be maintained in the study masterfile.

### 13. Statistical Considerations

#### **13.1 Sample Size Calculation**

Patients will be recruited over a whole year tentatively between February and December, 2016. It is estimated that 2-5 % of encountered patients are anemic and eligible for enrollment.

Assuming at 90 % power, 5 % level of significance, based on previous pilot study: a proportion of responders of 0.54 and a standard deviation of 1.21, a response rate of 50 % or more being clinically meaningful, and testing for superiority; a minim of 25 subjects are required. To account for a 10 % chance for drop-outs the required sample is adjusted to 47.5 and approximated to the nearest tens. A total of fifty subjects will be required for the assessment. Since, each strata will be analyzed separately, and assuming both follow the same assumptions 50 subjects per strata will be recruited to make a total study sample of one hundred..

Recruitment of 100 patients in 10 months is doable.

East 6.3 software was used in the estimation of sample size.

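### The stated 90% power does not follow from the plan's own inputs: 54% against 50% needs about 1,335 to 1,638 patients per stratum, and 25 plus 10% drop-out is 28, not 47.5

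*Protocol*

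**What the plan says.** Protocol 13.1 and the SAP section of the same name carry the same sample size paragraph.

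- Error rates: "Assuming at 90 % power, 5 % level of significance".
- Inputs, attributed to a pilot study: "a proportion of responders of 0.54 and a standard deviation of 1.21".
- Reference and aim: "a response rate of 50 % or more being clinically meaningful, and testing for superiority".
- Result and inflation: "a minim of 25 subjects are required. To account for a 10 % chance for drop-outs the required sample is adjusted to 47.5". The 47.5 is then rounded to 50, applied to each of the two iron-status strata, and doubled to 100.

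The paragraph writes no null hypothesis and does not name the test, its sidedness or the unit of the standard deviation. Response (an Hb rise of at least 1.0 g/dL) is the first of three primary endpoints in Protocol 6.3.1. Mean Hb change to week 12 is the third. The study has a single arm, and the strata are analysed separately.

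**The concern.** Two things fail on reading. First, a gap of four percentage points (54% against 50%) is very small for a one-sample test, and 25 patients cannot detect it with 90% power. Second, a 10% allowance cannot nearly double a sample.

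The paragraph also mixes two kinds of input. An SD of 1.21 has no place in a test of a proportion, because a 0/1 response with probability 0.54 has SD √(0.54 × 0.46) = 0.498.

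This is the only justification given for the sample size. A reader would take it that each stratum has 90% power on the response rate. If the pilot rate is true, a test against 50% in a stratum of 50 would fail 90% to 94% of the time. That failure would say little about whether the treatment works.

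**Working it through.** **Inputs** (Protocol 13.1): α = 0.05, power 0.90, p₁ = 0.54, SD 1.21, drop-out 10%. I take p₀ = 0.50 because it is the only reference rate named. Sidedness is not stated, so both cases are shown.

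**1. Trying to reproduce 25.** For a one-sample proportion test,

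n = [z_α √(p₀(1−p₀)) + z_β √(p₁(1−p₁))]² / (p₁−p₀)²

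- One-sided: [1.645 × 0.5 + 1.2816 × 0.4984]² / 0.04² = 1.4611² / 0.0016 = 1,334.3, so **1,335**.
- Two-sided: [1.960 × 0.5 + 1.2816 × 0.4984]² / 0.04² = 1.6187² / 0.0016 = 1,637.6, so **1,638**.

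Other versions agree. Using the alternative variance, a continuity correction or the arcsine transform gives 1,330 to 1,360 one-sided and 1,632 to 1,663 two-sided. An exact binomial search first reaches 90% at 1,350 and 1,649. None comes near 25 or 50.

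**2. Power the stated samples have** (exact binomial, null 0.50, true rate 0.54):

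| n | Test | Responders needed | Power at 0.54 |
|---|---|---|---|
| 25 | one- or two-sided | 18 | 5.2% |
| 50 | one-sided 5% | 32 | 10.0% |
| 50 | two-sided 5% | 33 | 5.8% |

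With n = 50, power reaches 90% only when the true rate is about 0.71 (one-sided) or 0.73 (two-sided).

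**3. The drop-out step.**

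- 25 / 0.9 = 27.8 and 25 × 1.1 = 27.5, so 28 either way.
- Backwards, 47.5 × 0.9 = 42.75 and 47.5 / 1.1 = 43.2. The implied base is about 43, a figure that appears nowhere.
- Going from 25 to 47.5 by drop-out alone needs 1 − 25/47.5 = 47%.

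**4. Could the SD of 1.21 rescue it?** Read as a one-sample mean test, n = (z_α + z_β)² SD² / δ², one-sided:

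- δ = 0.7 g/dL (pilot mean rise of 1.7 in Protocol 5.2, less the 1.0 response threshold): 2.926² × 1.21² / 0.7² = 25.6, so 26. This is near 25.
- δ = 0.54 g/dL (the proportion entered as a difference): 2.926² × 1.21² / 0.54² = 43.0. Adding 10% gives 47.3 (× 1.1) or 47.8 (/ 0.9), near 47.5.

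These use different effects, neither is stated as the design effect, and together they do not lead from 25 to 47.5. They show how such figures might arise and are conjecture.

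**5. What 50 per stratum delivers.**

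- Response rate: an observed 27/50 (54%) has an exact 95% CI of 39% to 68%. The approximate half-width is 1.96 × √(0.54 × 0.46 / 50) = 0.138.
- Mean Hb change, two-sided paired t-test at 5%, taking 1.21 as the SD of change in g/dL: 90% power for 0.57 g/dL.

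**The case against.** The strongest reply is that no null hypothesis is written, so 50% is a reading and the figures of 1,335 and 1,638 depend on it. That is fair, and those figures should be quoted as conditional. But no other reference rate is offered, and the drop-out error does not depend on any null.

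A second reply is that Protocol 13.2 and the SAP plan no test of the response rate against 50%. They plan paired t-tests of Hb against baseline and analyses of predictors of response. This too is correct. The harm is therefore not a planned test that will fail, but a power claim for a test the analysis plan does not contain. That leaves the claim with less support, not more.

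Third, the design is sounder than the paragraph suggests. On mean Hb change, with SD 1.21 g/dL, 50 patients give about 98% power for 0.7 g/dL. This stands, and it is why no larger sample is requested.

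Finally, 47.5 may be a simple slip. It equals 25 × 1.9, and it is one digit from 27.5. Either is possible. If 27.5 was meant, rounding to the nearest ten gives 30, and the 50 per stratum loses its derivation.

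**Conclusion.** The concern holds. Neither 25 nor 47.5 follows from the inputs printed beside it, in either document. If 50% is the null value, the stated 90% power is 5.2% at n = 25, and 10.0% (one-sided) or 5.8% (two-sided) at n = 50. The sample that would give 90% is 1,335 or 1,638 per stratum. The drop-out error, 28 against 47.5, holds on any reading.

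The power figures assume that 50% is the null value and the pilot rate of 0.54 is true. The mean-change figures assume that 1.21 is the SD of Hb change in g/dL, which the documents do not say. How the 25 and the 47.5 arose cannot be settled from the text, and the conclusion does not need it. This must be corrected, because the stated power for a primary endpoint is false as written. The sample of 50 per stratum is not itself shown to be unsuitable.

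**What to change.** Keep 50 per stratum and rewrite the paragraph identically in Protocol 13.1 and the SAP:

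1. Delete the claim of 90% power for 0.54 against 0.50, and the step from 25 to 47.5.
2. State which primary endpoint the sample size rests on, with its null value, test and sidedness. Give the unit and source of the SD of 1.21.
3. Say what 50 delivers. For the response rate: a 95% CI of about ±14 points and, if a test against 50% is wanted, 90% power only for a true rate of about 0.73 two-sided (0.71 one-sided). For mean Hb change: 90% power for 0.57 g/dL by a two-sided paired t-test, once the SD is confirmed.
4. If a test of the response rate against 50% is intended, add it to Protocol 13.2 and the SAP. If not, present the rate as an estimate with its interval.
5. Align the drop-out allowance with Protocol 8.3, which already replaces withdrawn patients until 50 per stratum are analysable.

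The cost is rewording in two documents and no extra patients. The sponsor gives up a favourable power statement that the inputs do not support.
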